# Table 8.

In addition, for selected variable sets, similar forest plots will be made comparing performance of the various estimated models (e.g., by individual learning algorithm types such as lasso), including discrete superlearner and superlearner models. The plot will be examined to determine which individual learning algorithm types are performing the best. If there is an interpretable algorithm that has performance close to the best-performing algorithm (which is most likely to be the superlearner), then it will be fit on the entire data set of vaccine recipients and the estimated model presented in a table.

Cross-validated ROC curves are plotted for the superlearner estimated models for each of the input variable sets. In addition, boxplots of cross-validated estimated probabilities of outcome by case-control status (as estimated from the superlearner models) are plotted.

# 12.6.5 [With Day 29 markers]

The weights  $\hat{w}_{57,x}$  are used even for models that include Day 29 markers but not Day 57 markers, because only primary cases (starting 7 days post Day 57 visit) are included in the multivariable CoR analyses. Thus the Superlearner analyses only used the weights  $\hat{w}_{57,x}$ .

Regarding the 12 variable sets listed above, additional variable sets will be included to represent Day 29 markers as input variables. In particular, variable sets 2–12 will only include Day 57 markers. These variable sets will be cloned into 11 new sets (13-23) including Day 29 markers in place of Day 57 markers. Lastly, another 11 variable sets (24–34) will be formed with the same structure, where each input variable set includes both Day 29 and Day 57 markers. This allows the Superlearning modeling to address whether including markers from both time points improves prediction of outcome. Therefore, if Day 29 markers are included, the number of input variable sets is 34 instead of 12.

## 12.6.6 Variable set and individual variable importance

The importance of variable sets (and individual variables) will be summarized by the estimated gain in population prediction potential (also referred to as the intrinsic importance) when comparing each variable set plus baseline risk factors to baseline risk factors alone. Prediction potential (predictiveness) will be measured using CV-AUC. Inference on the intrinsic importance will be based off sample splitting; thus, both the estimated variable importance and the estimated CV-AUC of each variable set when evaluated on independent data from the data used to evaluate the CV-AUC of the baseline risk factors will be reported. The class-balancing versions of SL.xgboost will be dropped from the Super Learner library in the variable importance computation as the regression carried out to account for the two-phase sampling will be based on a continuous outcome (so there won't be any imbalance).

## 12.7 Multivariable CoR: Multivariable Cox models

# 12.7.1 Objectives

A complementary analysis to the multivariable super learner analysis will use several multivariable Cox models to examine associations between sets of markers and the hazard of COVID-19. This approach has the benefit over super learner of targeting more interpretable measures of the relative importance of individual markers after adjustment for other markers. The motivation is to provide additional evidence as to whether and to what extent single vs. multiple markers exhibit stronger overall signal as a correlate.

# 12.7.2 Standardization of markers

In order for the magnitude of the estimated hazard ratios to be comparable across markers, we will standardize all markers prior to inclusion in the Cox model by scaling by their estimated standard deviation. Estimation of the standard deviation should take inverse probability weights into account.

## 12.7.3 Primary multi-variable Cox model

The primary multivariable models will be two models (one for Day 57 markers, one for Day 29 markers) fit as described in the univariable model section above, but adjusting for sets of markers. In particular, our primary model includes binding Ab to RBD, pseudovirus neutralization ID50, and live virus neutralization MN50. A Wald test using the robust variance estimator as implemented in the **survey** package will be used to evaluate the null hypothesis of no association between any marker and hazard of COVID-19. Hazard ratios will be reported per standard deviation increase alongside 95% confidence intervals.

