#### 4.3 Synthesis of the Phase 3 Correlates Analyses for Decisions

Establishment of an immunologic biomarker for approval/bridging applications is generally not based on pre-fabricated criteria nor a single type of correlates analysis. Therefore, the goal of the correlates analysis is to generate evidence about correlates from many perspectives, and to synthesize the evidence to support certain decisions. Consequently, we believe there is value in assessing all of the types of correlates presented in Table 1 in each trial, given that the analyses address distinct questions. Obtaining a set of results from multiple distinct approaches that provide complementary and coherent support may increase the rigor and robustness of an evidence package supporting potential use of an antibody marker as a validated surrogate (for traditional approval) or as a non-validated surrogate (for accelerated approval) (Fleming and Powers, 2012); these uses of a biomarker are summarized below. However, the assumptions needed for valid inferences are somewhat different across the methods, and some of these assumptions have testable implications; therefore examination of the assumptions may lead to favoring some methods over others, and affect the synthesis and interpretation of results, and moreover if diagnostics support that some necessary assumptions are infeasible then certain analyses will be canceled, as described below.

Section 16 summarizes the approach to use and interpretation of the set of multiple correlates of protection methods. Furthermore, depending on the number of study endpoints in the vaccine and placebo arms at the time a trial delivers primary results, some of the Day 57 marker correlates types defined in Table 1 will be evaluable at the first correlates analyses, whereas others will not be evaluable until additional evaluable vaccine breakthrough endpoints have been observed.

As detailed in Table 4, some CoR analyses are done after there are at least 25 evaluable vaccine breakthrough cases, which is considered to be a minimal number to achieve worthwhile precision. On the other hand, the most non-parametric/flexible CoR analyses require more cases, as do the CoP analyses in general, given the need to adjust for all potential confounders in order to fully identify the causal effects parameters of interest and the greater challenge in estimation (compared to CoR analysis) posed by the need to deal with missing potential outcomes.

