#### 6 Timeline/Sequencing of Correlates Analyses

The correlates analyses are initiated by the availability of (a) a data set defined at or after the primary analysis data set triggered by the accrual of a certain number of primary endpoints (typically approximately 150 in U.S. phase 3 studies); and (b) Day 1, 57 antibody marker data from correlateseligible COVID primary endpoint cases from at least 25 baseline negative vaccine recipients. The latter requirement ensures that there are enough endpoint cases to achieve worthwhile precision for CoR analyses. The HVTN 505 trial serves as a precedent where 25 evaluable vaccine recipient cases provided enough data to reasonably characterize correlates of risk for a preventive candidate HIV vaccine (Janes et al., 2017; Fong et al., 2018; Neidich et al., 2019; Gilbert et al., 2020b). In addition, simulation studies show that correlates analyses at 20 endpoints have notably lower precision.

Table 4 shows the minimum number of baseline negative vaccine recipient endpoints evaluable for correlates analyses that are required before conducting the various planned correlates analyses.

Correlates Analysis Type	Number
CoRs (Risk Prediction Modeling)	
a. (Semi)parametric models with strongly parametrized associations:	
Cox, hinge/threshold logistic regression	25
b. Flexible parametric models: Generalized additive model	35
c. Nonparametric thresholds: Donovan et al. $(2019)/$	
van der Laan et al. (2020)	35
d. Superlearner estimated optimal surrogate	35
CoP: Correlates of VE	50
CoP: Controlled VE	50
CoP: Stochastic Interventional VE	50
CoP: Mediators of VE	50

Table 4: Minimum Numbers of Evaluable Endpoints in Baseline Negative Vaccine Recipients toInitiate Correlates Analyses

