Henceforth we refer to the baseline variables that are adjusted for in correlates analyses as "baseline factors" which, depending on the risk score results and performance, will consist of only the individual key risk factors, or key individual risk factors plus the baseline risk score.

If a fully automated/pre-specified approach to defining the baseline factors is required, then the following approach will be used: Advance the risk score, the at-risk indicator, and the communities of color indicator. This choice is justified by the epidemiological data showing that these two indicators are strong infection and COVID-19 risk factors, and making use of the flexibility of super learner to develop a model for how age relates to risk.

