## 12.6.4 Implementation of superlearner

For baseline risk score development, Superlearner is applied to the placebo arm only, as mentioned in Section 10. For multivariable immune correlates of risk/estimated optimal surrogate development, Superlearner is applied to the vaccine arm only. The following details are used in the implementation of superlearner of the vaccine arm only:

- Pre-scale each quantitative and ordinal variable to have empirical mean 0 and standard deviation 1.
- For the immune correlates analysis, the final library of learners is selected

accounting for the number of phase-two endpoint cases in the vaccine arm. If the number of cases is limited, at or near 25 evaluable endpoint cases, then the modeling will only allow learning algorithms to have a maximum of 5 Day 57 antibody marker variables, and will use leaveone-out cross-validation and the negative log-likelihood loss function, a combination that tends to provide good performance in small sample size settings. On the other hand, if there are larger numbers of endpoint cases in the vaccine arm, then 5-fold cross-validation will be used, and no more than floor( $n_v/6$ ) input variables will be used in the model where  $n_v$  is the number of evaluable vaccine endpoint cases. The choices will be finalized prior to case/control unblinded analysis.

- Include learning algorithms with and without screening of variables. Screens used will be: 1) glmnet (lasso) pre-screening (with default tuning parameter selection), 2) logistic regression univariate 2-sided p-value screening (at level p < 0.10), and 3) high-correlation variable screening (described below). The adaptive algorithms (SL.randomForest, SL.xgboost, SL.gam, SL.polymars) are only used with these screens, given that the limited number of endpoint cases may challenge use of these methods with no variable screening. Moreover, the adaptive algorithms are not used if there are only 25 (or close to it) endpoint cases. All of the selected learners are coded into the SuperLearner R package available on CRAN.

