# 12.7.4 Secondary multi-variable Cox models

We fill additionally fit a series of exploratory, bivariate Cox models. These models will be fit as above but will include only two markers. The sets of two markers that we consider are

- 1. binding Ab to RBD and pseudovirus neutralization ID50
- 2. binding Ab to RBD and live virus neutralization MN50

As above, Wald tests will be used to evaluate the null hypothesis of no association between any marker and hazard of COVID-19. Hazard ratios will be reported per standard deviation increase alongside 95% confidence intervals.

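### The joint Wald tests in the multivariable Cox models have no small-sample reference or stated case minimum; at 25 cases the three-marker test has a simulated size of about 8% to 9% at a nominal 5%

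*Combined protocol and SAP*

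**What the plan says.** Section 12.7.3 specifies one model for Day 57 markers and one for Day 29 markers, fitted in the same way as the univariable Cox models. On content, "our primary model includes binding Ab to RBD, pseudovirus neutralization ID50, and live virus neutralization MN50". The test is "A Wald test using the robust variance estimator as implemented in the" survey package, and it "will be used to evaluate the null hypothesis of no association between any marker and hazard of COVID-19", so it is a joint test on 3 degrees of freedom. Section 12.7.4 adds two exploratory models with two markers each: "As above, Wald tests will be used to evaluate the null hypothesis of no association between any marker and hazard of COVID-19".

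The models also carry the baseline factors. The automated default in section 10 is "Advance the risk score, the at-risk indicator, and the communities of color indicator", which is three terms.

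On timing, section 4.3 says "some CoR analyses are done after there are at least 25 evaluable vaccine breakthrough cases". Table 4 in section 6 gives 25 for the row "Cox, hinge/threshold logistic regression" and 35 for the superlearner. Neither Table 4 nor Table 10 has a row for a multivariable Cox model. Footnote 3 of Table 10 says that only the superlearner combines assays.

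Section 12.4.2 applies its resampling adjustment to ten p-values, all from univariable Cox models.

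**The concern.** A Wald statistic with an estimated sandwich variance follows its chi-square reference only when there are many events. With few cases the variance of the marker coefficients is estimated imprecisely and tends to be too small. The effect grows with the number of coefficients tested together. Here three coefficients are tested, six are fitted, and the number of cases may be as low as 25. Nothing in 12.7 allows for this, and the resampling that could have done so stops at the univariable tests.

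Section 12.7.1 presents these models as additional evidence on whether single or multiple markers carry the stronger signal. A joint p-value that is too small near the minimum case count would overstate that evidence.

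**Working it through.** The SAP gives no type I error for this test, so there is no planned figure to reproduce.

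**Inputs from the SAP**
- Markers tested: q = 3 (12.7.3) or q = 2 (12.7.4).
- Baseline terms: 3 (section 10 default). Coefficients: p = 3 + 3 = 6, or 2 + 3 = 5.
- Subcohort of baseline-negative vaccine recipients: 150 × 6 strata = 900 (Table 5).
- Marker correlation: 0.7 base (simulation defaults, section 24.2.1).
- Variance: two-phase, sampling without replacement (12.3.3); the plain weighted sandwich was also run.

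**Assumptions not in the SAP**
- About 14,000 vaccine recipients (5,000 also tried).
- Stratum shares, covariate effects and follow-up pattern.
- All cases assayed, so case weight 1.
- Nominal level 5%, implied by the 95% confidence intervals.
- A chi-square reference, since 12.7.3 names none.

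**Statistic.** W = b′V⁻¹b, where b holds the q marker coefficients and V is their block of the robust variance. The test rejects if W exceeds the 95% chi-square point: 7.815 for q = 3, 5.991 for q = 2.

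**Simulated size under the null** (separately coded simulations; 20,000 runs has a Monte Carlo standard error of about 0.2 points)

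| Setting | Chi-square reference, nominal 5% |
|---|---|
| 3 markers, 25 cases | 8.3%, 8.6%, 8.8%, 8.9% |
| 3 markers, 35 cases | 6.9%, 7.1%, 7.2%, 7.5% |
| 3 markers, 50 cases | 5.9%, 6.2%, 6.6% |
| 3 markers, 100 cases | 5.4% |
| 2 markers, 25 cases | 7.4%, 7.5%, 7.6%, 7.9% |

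Variants at 25 cases with three markers ran from 7.9% to 9.3%. They covered correlation 0.5 and 0.9, a Poisson case count, 5,000 recipients, equal strata, 100 sampled per stratum, markers floored at a detection limit, a stronger risk-score effect and no link between age and marker. The two variance estimators gave the same answer (8.8% each). At a nominal 1% the size was 2.6% to 2.8%.

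**Closed-form check.** If W/q really behaves as F(q, d − p), with d cases, the size of the chi-square test is P(F > 7.815/3 = 2.605) for q = 3:
- d = 25: F(3, 19) gives 8.2%.
- d = 35: F(3, 29) gives 7.1%.
- d = 50: F(3, 44) gives 6.4%.
- q = 2, d = 25: P(F(2, 20) > 5.991/2 = 2.996) = 7.3%.

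These track the simulations closely, which supports this F as the working reference.

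**Size with the F(q, d − p) reference.** At 25 cases with three markers, runs gave 4.9% and 5.2%. At 35 cases one run gave 5.0%. Two markers at 25 cases gave 5.0% and 5.2%. A further set of runs over these settings and 50 cases gave 4.6% to 5.1%. The 5% cut-off for W rises from 7.815 to 3 × 3.127 = 9.38 at 25 cases.

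An F reference with a large design-based denominator of about 900 does not help: 8.7% to 8.8% at 25 cases.

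**The case against.** **The 25-case minimum is an inference.** Table 4 says only Cox, Table 10 lists only single-marker Cox rows, and 12.7.1 calls these models complementary to the superlearner, which needs 35 cases. Starting at 35 is a fair alternative reading. This stands. On that reading the size is about 7% to 7.5%: smaller, but not removed.

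**The primary model may not run at the first analysis.** It needs MN50, and 12.4.2 allows for MN50 arriving later. Until then only the exploratory RBD plus ID50 model could be fitted. This also stands. The Day 29 model counts intercurrent cases as well, so it has at least as many cases as the Day 57 model, and 25 is a floor rather than an expected count.

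**No decision rule uses this p-value.** No alpha is stated for it, the flags in 12.4.2 apply to the ten univariable p-values, and section 16.1 relies on human synthesis. That limits the consequence. It does not make the p-value correct as specified.

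**A stronger reading that fails.** A reader might infer that the model breaks the plan's own allowance of one variable per six cases. In 12.6.4 the floor(n/6) limit, where "input variables will be used in the model" are capped, applies to the superlearner when there are larger numbers of cases. At or near 25 cases the cap is five Day 57 marker variables, and this Cox model has three. The documents show no breach.

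**Conclusion.** The point holds. As written, the joint tests in 12.7.3 and 12.7.4 reject too often when cases are few. For three markers at a nominal 5%, the size is about 8% to 9% at 25 cases, about 7% to 7.5% at 35 and about 6% to 6.6% at 50. For two markers it is about 7.4% to 7.9% at 25. The excess has nearly gone by 100 cases.

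These are simulation results under the assumptions listed, not figures in the SAP, and the calibrated-weights option of 12.3.3 was not simulated. A reader might infer that the first analysis will certainly report a primary p-value with this error. The documents do not support that: the case count may exceed the minimum, the minimum is itself unstated for these models, and MN50 may be missing. The defect is a moderate size error in a supportive test that the SAP names as its primary multivariable Cox test. It should be corrected because the correction is easy.

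**What to change.** 1. In 12.7.3 and 12.7.4, state that W/q is referred to F(q, number of cases minus number of coefficients). Alternatively, take the p-value from joint resampling of the marker rows, extending the approach in 12.4.2. The F reference is better supported: the resampling was checked in only 400 trials (5.0%), where the Monte Carlo standard error is √(0.05 × 0.95/400) = 1.1 points.
2. Add the multivariable Cox models to Tables 4 and 10 with an explicit case minimum, and amend footnote 3 of Table 10 to match. Adopting 35 would align them with the superlearner but would leave the size at about 7% to 7.5% without step 1.

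The cost is a few sentences of SAP text and a small change to how the p-value is computed. P-values become slightly less favourable: with three markers and 25 cases, a result at exactly p = 0.05 under chi-square becomes p = 0.08.

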#### 12.5.3 Multi-variable extension

The above method extends naturally to multivariable models described below, where a standardized association is computed by multiplying the generalized Wald statistic by the number of "phase 2 ptids".

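### The primary three-marker Cox model has no test of whether two markers add to the third, and its global Wald test does not address single versus multiple markers

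*Combined protocol and SAP*

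**What the plan says.** Section 12.7.1 gives the multivariable Cox models two purposes. One is to obtain "more interpretable measures of the relative importance of individual markers after adjustment for other markers". The other is evidence on "whether and to what extent single vs. multiple markers exhibit stronger overall signal as a correlate".

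Section 12.7.3 specifies the primary model, fitted separately for Day 57 and Day 29: "our primary model includes binding Ab to RBD, pseudovirus neutralization ID50, and live virus neutralization MN50". One hypothesis test is named, a Wald test with the robust variance that "will be used to evaluate the null hypothesis of no association between any marker and hazard of COVID-19". The next sentence adds estimates: "Hazard ratios will be reported per standard deviation increase alongside 95% confidence intervals".

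Section 12.7.4 adds two exploratory two-marker models, RBD with ID50 and RBD with MN50, with the same test and the same estimates: "As above, Wald tests will be used to evaluate the null hypothesis of no association between any marker and hazard of COVID-19".

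Two other sections bear on the question. Section 12.5.3 carries the standardized-association comparison over to these models: "The above method extends naturally to multivariable models described below, where a standardized association is computed by multiplying the generalized Wald statistic by the number" (the multiplier being the phase-two sample size). Section 12.6 compares superlearner variable sets with one and with several immunoassays by CV-AUC. Section 12.7 itself gives no nested test and no rule for reading its results.

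**The concern.** Whether several markers do better than one is a nested question: given one marker, do the others add anything? The test in 12.7.3 is of all three coefficients equal to zero. That is false when a single marker is a correlate, which the univariable Cox models of 12.3.3 already test. A small p-value therefore fits a one-marker truth and a several-marker truth about equally well.

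The distinction matters because Section 5 prefers a correlate built on a single assay unless combining assays improves it substantially. A reader could take a significant three-marker test as support for a multi-marker correlate when the second and third markers contribute nothing.

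**Working it through.** Section 12.7 states no power, sample size or alpha, so there is no planned figure to reproduce.

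**Inputs from the SAP.** Three markers in the primary model (12.7.3), so the global test has 3 df. A minimum of 25 vaccine-arm cases for Cox analyses (Table 4); 50 and 100 are also shown. Correlation ρ = 0.7 among RBD, ID50 and MN50 at Day 57, which is the simulation default for baseline-negative vaccine recipients (24.2.1). The higher defaults there apply to Spike with RBD and ID50 with cID80, pairs that no 12.7 model contains.

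**Assumptions.** Level 0.05; hazard ratio per SD of 0.5 (0.6 and 0.7 as variants); ρ = 0.9 as an upper case, since 12.4.2 expects high and possibly very high correlations without giving a value; no information lost to sampling weights.

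**Model.** With d events and marker correlation matrix R, the estimated log hazard ratios are approximately N(b, R⁻¹/d). A Wald test is then noncentral chi-square with noncentrality λ.

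**Step 1. Global test, one true marker.** b = (ln HR, 0, 0), so λ = d(ln HR)², whatever ρ is. The 3-df critical value is 7.815.
- HR 0.5, d = 25: λ = 25 × 0.4805 = 12.01, power 84%.
- HR 0.5, d = 50: λ = 24.02, power 99%.
- HR 0.6: 56% at 25 events, 87% at 50.
- HR 0.7, d = 25: 29%.

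**Step 2. Global test, two equal contributors, each with marginal HR 0.5.** Each coefficient is β = ln 0.5/(1+ρ), and λ = 2d(ln 0.5)²/(1+ρ).
- d = 25: λ = 14.13 at ρ = 0.7 (90%) and 12.64 at ρ = 0.9 (86%).
- d = 50: 99–100%.

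Against 84% and 99% in step 1, the global test hardly separates the two situations.

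**Step 3. Nested 2-df test of the other two markers given the first.** The critical value is 5.991. With one true marker and that marker conditioned on, λ = 0 and the test rejects 5% of the time. With two equal contributors, conditioning on one of them, λ = dβ²(1−ρ²) = d(ln 0.5)²(1−ρ)/(1+ρ).

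| Events | λ, ρ = 0.7 | Power | λ, ρ = 0.9 | Power |
|---|---|---|---|---|
| 25 | 12.01 × 0.3/1.7 = 2.12 | 24% | 0.63 | 10% |
| 50 | 4.24 | 44% | 1.26 | 16% |
| 100 | 8.48 | 74% | 2.53 | 28% |

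**Step 4. What the separate CIs deliver.** With three equally correlated markers the variance inflation is (1+ρ)/[(1−ρ)(1+2ρ)]: 1.7/(0.3 × 2.4) = 2.36 at ρ = 0.7 and 1.9/(0.1 × 2.8) = 6.79 at ρ = 0.9. With one true marker at HR 0.5, its adjusted CI excludes 1 in 62% (ρ = 0.7) or 27% (ρ = 0.9) of trials at 25 events, and in 89% or 47% at 50.

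At HR 0.6, among trials where the global test rejects, all three CIs still include 1 in 34% (25 events) and 24% (50 events) at ρ = 0.7, and in 64% and 62% at ρ = 0.9.

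**Check.** Unweighted Cox fits to simulated data (1000 subjects, 600 replicates, one true marker at HR 0.5) gave global rejection of 82–83% at 25 events and 99% at 50, and nested rejection of 4.2–6.3%.

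**The case against.** The strongest reply is that the plan does not rest on the global test. An adjusted 95% CI is a 1-df Wald test of that marker given the others. In the two-marker models of 12.7.4 this is exactly the added-value test, so those models lack only a sentence on how to read it. This stands. A reader might infer that the 12.7 models cannot answer their own question; the CI output contradicts that.

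A reader might also infer that the SAP never compares one assay with several. It does: 12.6 plans CV-AUC comparisons partly for that purpose, and 12.7.1 calls the Cox models complementary to them. Nor does any flag depend on the global test, since 12.4.2 builds its flags on ten univariable p-values.

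The reported CIs would also often point the right way. At HR 0.6, 50 cases and ρ = 0.7, when the global test rejects, only the true marker's CI excludes 1 in about 66% of trials; two or more CIs do so in about 7%.

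This leaves the three-marker model uncovered. No single CI gives the joint test of two markers given the third, and no two-marker model pairs ID50 with MN50. Section 12.5.3 does not supply the test. It multiplies the Wald statistic by a sample size where 12.5.2 divides by a sample-size term, and it makes no allowance for degrees of freedom, although the null expectation is 3 on 3 df against 1 on 1 df.

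**Conclusion.** The concern holds for the primary three-marker model. Its one named test does not address single versus multiple markers, and neither the separate CIs nor 12.5.3 gives a joint added-value test. At an assumed HR of 0.5 per SD and 25 events, the global test rejects 84% of the time with one true marker and 86–90% with two.

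It would be too strong to say that the global test rejects whenever one marker is a correlate. The null is then false, but rejection depends on power: 29% at HR 0.7 with 25 events.

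The rates rest on assumed hazard ratios, correlations of 0.7 to 0.9 and no loss of information from weighting. That the global test answers a different question depends on none of these. The gap is one of specification in a supportive analysis.

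**What to change.** In 12.7.3, pre-specify from the same fitted model the 2-df Wald test of the other two markers given each marker in turn (three tests, same robust variance). In 12.7.4, state that each marker's adjusted hazard ratio CI is read as the test of its added value given the other marker. State in both sections that the global test alone is not evidence for a multi-marker correlate.

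The cost is SAP wording and a few more p-values, to be labelled exploratory; no new model or data are needed. The SAP should also acknowledge the low power shown above and say that a non-significant nested test does not establish that one marker is enough.
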